AUC _{0-last}	Area under curve from time 0 to time of last measurable concentration.
AUC _{0-inf}	Area under curve from time 0 to infinity
BOR	Best overall response
BSA	Body surface area
CI	Confidence interval
CL	Systemic clearance
C _{max}	Maximum observed plasma concentration
CR	Complete remission
CRh	CR with partial hematological recovery
Cri	CR with incomplete hematological recovery
C _{ss}	Observed concentration at steady state
CTCAE	Common terminology criteria for adverse events
DHO	Dihydroorotate
DHODH	Dihydroorotate dehydrogenase
DLT	Dose-limiting toxicity
DNA	Deoxyribonucleic acid
DOT	Duration of response
ECG	Electrocardiogram
ECOG	Eastern Cooperative Oncology Group
eCRF	Electronic case report form
EFS	Event-free survival
FISH	Fluorescence in situ hybridization
Hgb	Hemoglobin
mg	Milligram
m ²	Meters squared
MedDRA	Medical dictionary for regulatory affairs
MLFS	Morphologic leukemia-free state
NCI CTCAE	National Cancer Institute Common Terminology Criteria for Adverse Events
ORR	Overall response rate
OS	Overall survival
PK	Pharmacokinetic(s)
PR	Partial remission
PT	Preferred term
SAP	Statistical analysis plan
SI units	International system of units
SOC	System organ class
t _{1/2}	Elimination half-life
T _{max}	Time to maximum plasma concentration
TEAE	Treatment-emergent adverse event
TI	Transfusion independence
TLF	Tables, listings, and figures

I. Introduction

This Statistical Analysis Plan (SAP) presents details of the analyses required to address the study aims of [protocol CCB-01 version 6.0](#), dated 30 April 2019. The study is a phase 1b/2a open-label, multi-center trial with a purpose to evaluate the safety, efficacy, and pharmacokinetics (PK) of the drug oral brequinar in subjects 18 years or older with relapsed/refractory acute myeloid leukemia (AML), as well as to determine the inhibitory level of brequinar in blocking the enzyme “dihydroorotate dehydrogenase” (DHODH).

Safety and tolerability of brequinar will be assessed via adverse event (AE) monitoring, clinical laboratory safety tests, physical examinations, vital signs measurements, 12-lead electrocardiogram (ECG) readings, and bone marrow sampling. Specific efficacy endpoints of disease response, and PK profiles of brequinar and dihydroorotate (DHO) plasma levels will also be characterized.

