This SAP has been developed and approved prior to database lock and data analysis. All analyses will be conducted after clinical trial data are entered into the database, discrepancies resolved, and the database is authorized (closed to further changes). Any deviations from the SAP will be documented as such in the study report.

Production and quality control of statistical analyses and accompanying tables, listings, and figures (TLFs) will be the responsibility of IQVIA Biotech located in Morrisville, North Carolina, United States.

II. Protocol Objectives

A. Primary

The protocol lists the following primary objective:

- To determine the safety and tolerability of brequinar and the DHODH inhibitory activity of brequinar in adult subjects with AML.

B. Secondary

The protocol lists the following secondary objectives:

- To determine the overall response rate (ORR) including complete remission (CR), CR with incomplete hematologic recovery (CRi), morphologic leukemia-free state (MLFS), partial remission (PR) (criteria as defined in the ELN Guidelines, by [Dohner et al., 2017](#)) and complete remission with partial hematological recovery (CRh).

- To assess the rate of overall survival (OS) and event-free survival (EFS).
- To evaluate duration of response (DOR).
- To characterize the pharmacokinetic (PK) profile of brequinar.
- To characterize the DHO plasma levels after oral dosing with brequinar.

C. Exploratory

The protocol lists the following exploratory objectives:

- To assess the relationship between DHODH inhibition and the efficacy and safety of brequinar.
- To evaluate molecular and cellular biomarkers that may be predictors of antitumor level and/or treatment resistance including cytogenetics, molecular profiling, and flow cytometry during and after treatment.
- To evaluate global gene expression profiles, deoxyribonucleic acid (DNA)methylation profiles, and other potential prognostic markers to explore predictors of antitumor activity and/or resistance to treatment.

III. Study Endpoints

A. Primary Endpoints

The study protocol defines primary endpoints as safety/tolerability and DHO level relationship with safety and therapeutic brequinar levels.

Safety/tolerability, assessed at each study visit using the Common Terminology Criteria for Adverse Events (CTCAE) version 4.03, will be evaluated for each subject as follows:

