- AML supplemental tests: Cytogenetics and molecular data information recorded on the eCRF will be listed, including information on karyotypic, Fluorescence in situ hybridization (FISH), and gene fusion analysis, as well as all present mutations.
- Prior cancer drug treatment: A listing will display all entries for prior cancer medications received by a subject, ordered by “Start date”. A summary table will summarize the following characteristics:
 - Number of subjects reporting at least one prior cancer drug treatment.
 - Drug treatment type (Chemotherapy, Targeted therapy, Immunological, Not Applicable).
 - Drug treatment combined with radiotherapy (No/Yes).
 - Number of cycles received.
 - Best response under treatment (Complete remission, Complete remission with incomplete hematologic recovery, Complete remission with partial hematologic recovery, Morphologic

leukemia-free state, Partial remission, Stable disease, Progressive disease, Unknown).

- Relapse (derived as ‘Yes’ if date of relapse is not blank. ‘No’ otherwise).
- Prior cancer non-drug treatment: All non-drug treatments received will be listed in order of “Start date”. Summary statistics will be provided for:
 - Number of subjects reporting at least one prior cancer non-drug treatment.
 - Treatment type (Radiation, Surgery, Other).
 - Intention (Palliative, Therapeutic).
 - Best response under treatment (Complete remission, Complete remission with incomplete hematologic recovery, Complete remission with partial hematologic recovery, Morphologic leukemia-free state, Partial remission, Stable disease, Progressive disease, Not applicable, Unknown).
 - Relapse (derived as ‘Yes’ if date of relapse is not blank. ‘No’ otherwise).

D. Protocol Deviations

A listing will be provided for all protocol deviations.

VII. Safety Analyses

To meet the primary objective of the study, all safety analyses will be performed on the Safety Analysis Set of subjects.

A. Exposure

For each subject, the assigned dose level of brequinar (mg/m^2), the assigned dose (mg), dose day, date and time taken, whether entire dose was taken, number of capsules taken, total dose taken (mg), and the reason for missed dose (partial or complete) will be listed by treatment group and visit cycle.

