Summary statistics will be presented for assigned dose level, cumulative assigned dose, cumulative actual exposure (mg), total duration of treatment (calculated as the number of weeks from date of first drug dose to date of last drug dose), dose intensity (calculated as cumulative actual exposure divided by treatment duration, mg/week), relative dose intensity (calculated as a percent of cumulative actual drug dose divided by cumulative assigned dose), and any reason for missed dose.

B. DHO Plasma Levels

In addition to safety/tolerability, intra-subject dosing for this study will be guided by DHO levels measured using a validated assay. A subject listing will include baseline and trough DHO levels (ng/ml), as well as the following additional characteristics noted at each scheduled visit:

- Previous assigned dose (mg/m²).
- DHO dose adjustment (dose not changed, escalated by 150 mg/m², held, Cohort 1 dose escalation not permitted).
- Assigned dose based on DHO (mg/m²).
- PI evaluation of whether subject has acceptable safety, safety dose adjustment, and assigned dose.
- Actual dose (mg).
- Agreement between PI assessment and actual dose (No/Yes, reason for disagreement).

The above dose-modification characteristics will also be summarized by treatment group and overall.

C. Dose Limiting Toxicities

AEs identified as protocol-defined DLTs will be listed and will include start and end dates, CTCAE grade, relationship to study drug, outcome, and action taken. Number and percentage of subjects reporting DLTs in each treatment group, and overall, will be summarized.

D. Adverse Events

AEs will be collected from time of informed consent through at least 14 days after the final dose of study medication. Any pre-existing condition that changes in severity after dosing or abnormal laboratory finding will be recorded as an AE. Events that occur prior to dosing will be recorded as medical history. A TEAE for this study will be defined as an AE occurring after the first dose of the study treatment through 30 days after the last dose of study treatment.

Verbatim terms on the eCRF will be coded using the MedDRA version 21.1 and displayed hierarchically by system organ class and preferred term. Multiple incidences of the same AE for a subject will be counted only once at the maximum CTCAE grade.

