Duration of Response: Duration of response will be defined as the time from the first occurrence of a qualifying response of CR, CRi, CRh, MLFS, or PR, to the date when progressive disease is objectively documented or death due to any cause, whichever occurs earlier. Following the qualifying response, subjects who are alive without disease progression will be right-censored at the date of last disease evaluation. A Kaplan-Meier graph will be plotted by treatment group and estimates of median duration with associated 95% CIs will be reported.

Event-free Survival (EFS): Event-free survival will be determined from the first dose of brequinar to the date of relapse ($\geq 5\%$ bone marrow blasts, reappearance of blasts in blood, or development of extramedullary disease), disease progression, or death, whichever occurs first. Subjects who do not experience any of the three events will be right-censored at the latter date of disease evaluation or bone marrow sampling. A Kaplan-Meier graph will be plotted for time to the composite outcome by treatment group, and the estimate of medial survival time with 95% CI will be summarized.

Overall Survival (OS): Overall survival will be calculated as the time from the first dose of study drug to the date of death or right-censoring at the date of last subject contact. Median time to OS, with 95% CI, will be summarized and displayed graphically by treatment group using the Kaplan-Meier method.

B. Clinical Benefit

In addition to ORR, this study will examine clinical benefit to subjects. By treatment group, a summary table will report counts and percent of transfusion-dependent subjects at baseline who, in the absence of progression, CR or PR, and independent of marrow response, achieve one of the following:

- Erythroid response: Transfusion Independence (TI) for 8 or more weeks for subjects requiring at least 4 units of packed red blood cell transfusions in the previous 8 weeks. Only red blood cell transfusions given based on physician's judgment for a pretreatment hemoglobin (Hgb) of ≤ 8.5 g/dL will count in the red blood cell TI response evaluation.
- Platelet response: TI for subjects requiring a minimum of 4 platelet transfusions in the previous 8 weeks.

IX. Pharmacokinetic Analyses

The plasma PK of brequinar and DHO will be characterized using non-compartmental analysis. Where possible, the following standard PK parameters will be calculated:

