- $AUC_{0-\text{last}}$: Area under plasma concentration-time curve from time 0 to time of last measurable concentration.

- $AUC_{0-\infty}$: Area under plasma concentration-time curve from 0 to infinity.
- C_{\max} : Maximum observed plasma concentration.
- C_{ss} : Observed plasma concentration at steady-state.
- CL : Systemic clearance.
- T_{\max} : Time to maximum plasma concentration.
- $T_{1/2}$: Elimination half-life
- V_{ss} : Volume of distribution at steady state.

Listings of PK concentration and parameters will be generated using the Pharmacokinetic Analysis Set of subjects. Concentration and PK parameters will also be tabulated and summarized by treatment group at baseline and scheduled time points using descriptive statistics.

A listing of derived time interval between Brequinar dosing and pre-dose PK sampling will be provided.

Mean concentration-time profiles by treatment group, as well as by-subject plots for observed concentrations of brequinar and DHO levels will be presented on linear and semi-logarithmic scales.

Relationship between PK parameters, DHO levels, and clinical outcomes (e.g. efficacy, toxicity) may be explored.

X. Exploratory Analyses

This study will endeavor to explore the following aims:

Relationship between DHODH inhibition and the efficacy and safety of brequinar:

Identify molecular and cellular biomarkers predictive of antitumor level and/or treatment resistance including cytogenetics, molecular profiling and flow cytometry during and after treatment:

Evaluate global gene expression profiles, DNA methylation profiles, and other potential prognostic markers as predictors of antitumor activity and/or resistance to treatment.

XI. Changes from Analyses Planned in Protocol

There are no significant changes to the analyses planned in the study protocol.

XII. References

1. CCB-01 Protocol_ver_5_16OCT2018-FINAL.pdf
2. CCB-01 Protocol_ver6_30APR2019 FINAL_signed 15MAY2019.pdf

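### The SAP plans systemic clearance and Vss for brequinar, but oral data without an intravenous reference give only CL/F and an apparent volume; the shared list also needs a line on what applies to DHO (minor)

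*SAP*

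**What the plan says.** Section IX (Pharmacokinetic Analyses) states: "The plasma PK of brequinar and DHO will be characterized using non-compartmental analysis". It continues: "Where possible, the following standard PK parameters will be calculated". A single list follows, not divided by analyte. It contains AUC0-last, AUC0-inf, Cmax, Css, CL, Tmax, half-life and Vss. CL is defined there as "Systemic clearance", and the abbreviation list defines it the same way. Vss is defined as "Volume of distribution at steady state". The parameters are to be listed, tabulated and summarized by treatment group, and Section V.F adds geometric means and geometric CV% for PK parameters.

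On route, Section I describes "the drug oral brequinar in subjects 18 years or older", and Section VII.A (Exposure) records the number of capsules taken. The SAP mentions no intravenous dose and gives no value of F. The terms CL/F and Vz/F do not appear.

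On DHO, one of the secondary objectives in Section II.B is: "To characterize the DHO plasma levels after oral dosing with brequinar". DHO is thus measured after brequinar and is not itself given. Section VII.B lists a baseline DHO level for each subject. Section IX mentions no baseline correction of DHO parameters.

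**The concern.** Systemic clearance and Vss describe drug that has reached the circulation. After an oral dose the amount that reaches it is F times the dose. With F unknown, non-compartmental analysis can identify clearance and volume only up to the factor F. The volume has a second problem: the time a dose spends being absorbed enters the mean residence time from which Vss is computed.

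The brequinar PK profile is a named secondary objective. If the plan is followed as written, the report will show a column headed systemic clearance that holds CL/F, and a column headed Vss that holds neither Vss nor Vss/F. A reader who compares these with intravenous values would be misled. The CV% reported for CL would also mix between-subject variation in clearance with variation in bioavailability.

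The same list is applied to DHO. Without a DHO dose there is no numerator for clearance or volume, and with a persistent non-zero baseline an AUC extrapolated to infinity has no finite value.

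**Working it through.** The SAP states no figure on this point, so there is nothing to reproduce. It also gives no formulas. I assume the usual non-compartmental ones, CL = Dose/AUC0-inf and Vss = Dose·AUMC/AUC², where AUMC is the area under the first-moment curve.

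**Inputs from the SAP:** oral route (Section I), capsules (Section VII.A), no intravenous reference, no F, DHO not dosed (Section II.B), baseline DHO recorded (Section VII.B).

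**Assumed for illustration only:** a one-compartment oral model with true CL = 1, V = 20 and Dose = 1000 in arbitrary units; F from 0.3 to 1.0; absorption rate ka from 0.2 to 1.0 per hour.

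**Step 1, brequinar clearance.** After an oral dose AUC0-inf = F·Dose/CL, so Dose/AUC0-inf = CL/F. The ratio to systemic clearance is 1/F.

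**Step 2, brequinar volume.** After an oral dose AUMC/AUC = MRT + MAT (mean residence time plus mean absorption time). Hence Dose·AUMC/AUC² = (CL/F)·(MRT + MAT). Since Vss = CL·MRT, the ratio to true Vss is (1/F)·(1 + MAT/MRT). Here MRT = V/CL = 20 h and MAT = 1/ka, which is 1 h at ka = 1.0, 2 h at ka = 0.5 and 5 h at ka = 0.2. At F = 1 the ratios are 1 + 1/20 = 1.05, 1 + 2/20 = 1.10 and 1 + 5/20 = 1.25. Numerical integration of the concentration curve gives the same values:

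| Assumed F | Dose/AUC ÷ true CL | Moment 'Vss' ÷ true Vss (ka 1.0 / 0.5 / 0.2 per h) |
|---|---|---|
| 0.3 | 3.33 | 3.50 / 3.67 / 4.17 |
| 0.5 | 2.00 | 2.10 / 2.20 / 2.50 |
| 0.7 | 1.43 | 1.50 / 1.57 / 1.79 |
| 0.9 | 1.11 | 1.17 / 1.22 / 1.39 |
| 1.0 | 1.00 | 1.05 / 1.10 / 1.25 |

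The clearance column reaches 1.00 at F = 1; the volume column does not.

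**Step 3, the replacement volume.** Vz/F = Dose/(λz·AUC0-inf), with λz the terminal slope. In the same model λz = CL/V = 0.05 per hour, so Vz/F = (CL/F)/0.05 = 20/F. It carries the factor 1/F, as its name says, and no absorption-time term, provided the terminal slope reflects elimination.

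**Step 4, DHO.** CL and volume need a dose, and none exists. For the AUC, take an illustrative constant baseline b = 10 plus a decaying excess 1000·exp(−0.05t). Then AUC0-T = 10·T + (1000/0.05)·(1 − exp(−0.05·T)). This gives 20540 at 84 h, 21676 at 168 h, 23360 at 336 h and 26720 at 672 h. The last increase, 26720 − 23360 = 3360, equals 10 × 336 and is therefore all baseline. The excess part alone converges to 1000/0.05 = 20000. The uncorrected AUC keeps growing with the end time.

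**The case against.** The strongest defence is that little turns on this. The number in the clearance column is Dose/AUC whatever it is called, so the fix to CL is a change of label. PK parameters receive descriptive statistics only. The individual dose adjustment outlined in Section IV.A uses brequinar PK and DHO levels and mentions neither CL nor Vss. Relating PK parameters to outcomes is only something that may be explored. All of this stands, and it sets the severity. It does not remove the error, because the label determines what a reader may conclude about clearance, and for volume the reported number itself changes.

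The words Where possible could be read as a safeguard. For brequinar they are not: both quantities can be computed from an adequate oral profile and would be tabulated under the wrong names. For DHO the defence has more force, because a parameter that needs a dose is not possible for an analyte that is not dosed. A reader might infer that the SAP commits to reporting DHO clearance and Vss. The text does not support that; it shows a list that should have been split by analyte.

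Three further readings go too far:

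- A reader might take a figure such as 11% at F = 0.9 or 100% at F = 0.5 as the error in this trial. Both are 1/F − 1 at an assumed F. The SAP gives no F, and at F = 1 the clearance error is zero.
- A reader might infer that an uncorrected DHO AUC understates the relative effect in subjects with high baseline DHO. Section IX plans no relative-effect measure based on AUC, and a high baseline adds area. All that can be said is that the uncorrected AUC mixes baseline with drug effect.
- A reader might infer that dosing decisions are affected. Nothing in the SAP shows this.

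That DHO is endogenous is also an inference, drawn from its having a baseline and not being dosed; the SAP does not use the word.

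**Conclusion.** The point holds for brequinar as a minor error. Section IX names two quantities that oral data without an intravenous reference cannot give. Dose/AUC is CL/F, and it differs from systemic clearance by a factor 1/F of unknown size, equal to 1 if F = 1. The moment-based Vss is wrong even at F = 1, by a factor 1 + MAT/MRT, which is 1.05 to 1.25 under the assumed model and absorption rates. These sizes rest on assumptions outside the SAP; the identities behind them do not.

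For DHO the point is narrower. The shared list does not say which parameters apply to an analyte that is not dosed and has a baseline, and AUC0-inf over a non-zero baseline is not a meaningful quantity.

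**What to change.** In Section IX, for brequinar, replace CL (systemic clearance) with CL/F (apparent oral clearance) and Vss with Vz/F (apparent volume in the terminal phase). Correct the CL entry in the abbreviation list to match and add Vz/F there.

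Give DHO its own line. State that clearance, volume and AUC0-inf do not apply. Report AUC over a stated fixed interval with baseline correction, alongside the observed DHO values that the SAP already plans to list and summarize. The same line can say whether half-life and Css are intended for DHO.

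The cost is SAP wording and a small change to parameter programming and table shells. No new data are needed. The brequinar clearance values stay the same under a correct name, and the volume values change.

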Up to 27 subjects are planned to be entered in this trial. Cohort 1 was planned to have 6 subjects, but enrollment was stopped after 5 subjects when brequinar PK and DHO results became available. These results led to study design changes as described here. The sixth subject will not be enrolled in Cohort 1.

Cohort 2 will enroll approximately 6 subjects, followed by an expansion cohort of approximately 15 subjects. All subjects in Cohort 2 will start with a 500 mg/m² dose once-weekly. Brequinar PK and DHO samples will be obtained for these subjects in Week 1 and results used to make decisions about the Week 2 once-weekly dose. Brequinar PK and DHO samples will also be obtained for Week 2 and the results used to make decisions about Week 3 dose frequency (once or twice-weekly) and the dose. The dose will be adjusted for each subject to meet the twice-weekly brequinar PK and 72-hour DHO criteria, and the Week 2 procedures may be repeated if needed until the twice-weekly dose is found.

After both the brequinar PK and 72-hour DHO level meet criteria described in the Individual Dose Adjustment Guidelines as described in Protocol Section 8.5, a subject may move to twice-weekly dosing on a continuing basis as tolerated. The twice-weekly dose may be further adjusted using 84-hour DHO (trough ~ 84 hours after dosing) criteria, also described in the Guidelines for Individual Dose Adjustment.

Dosing will continue up to 12 months in the absence of unacceptable toxicity or disease progression, or may be discontinued with Sponsor consent after completing at least 6 weeks of dosing.

B. Study Population

Up to 27 subjects 18 years or older with relapsed/refractory AML by World Health Organization (WHO) classification who have exhausted available therapy and who meet all inclusion/exclusion criteria will be enrolled at 3- 6 sites in the United States.

C. Sample Size Predictions

Formal sample size calculations are not applicable to this phase 1b/2a dose-adjustment and expansion study.

V. General Analytical Considerations

All analyses of safety and anti-leukemic activity for this open-label, early-phase study will be descriptive in nature and presented by dose group and overall, as appropriate, for dose-adjustment and expansion phases.

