Statistical code and outputs for analyses will be generated using SAS/STAT and SAS/GRAFH software, version 9.3 or higher, of the SAS system for Windows. Copyright © [2011] SAS Institute Inc. SAS and all other SAS Institute Inc. product or service names are registered trademarks or trademarks of SAS Institute Inc., Cary, NC, USA.

A. Data Sources

The study center staff will record completion and results of required study procedures in an electronic case report form (eCRF). The following external data obtained from third-party vendors for this study will be combined with eCRF data for analysis:

Vendor Name	Contact Information	Data Type	Schedule	Reconciliation Items
Pyxant	TBD	DHO plasma levels and brequinar PK results	2 transfers during study	Header data (subject ID, initials, visit, lab date, lab time)

B. Multiple Study Centers

Data analyses will be pooled and not controlled for center effect.

C. Definition of Baseline

Baseline will be defined as the last measurement collected before the first dose of study drug. As such, height and body surface area assessed at Screening, and pre-dose assessments made on Cycle 1 Week 1 Day 1 for weight, vital signs, hematology/chemistry, and 12-lead ECG will serve as valid baseline measures. A missing value at Cycle 1 Week 1 Day 1 will default to the Screening measurement.

For this study, since there is no day 0, the day immediately prior to study day 1 will be Day -1 [calculated as Event Date – Date of First Treatment]. For events on or after first dose of study drug, study day will be calculated as [Event Date – Date of First Treatment + 1]. Thus, first day of study drug dose will be Day 1.

D. Missing Data

Unless stated otherwise in sections below, missing data will not be replaced with imputed values.

E. Analysis Populations

Four analysis population sets will be defined for use with various analyses, namely:

- The Enrolled Analysis Set will include all subjects who sign informed consent, meet the inclusion/exclusion criteria and are enrolled in the study. Demographics and disposition summaries will be reported for this set of subjects.
- The Safety Analysis Set will include all subjects who are enrolled in the study and receive at least one dose of brequinar. Subjects in this set will be used for all safety/tolerability summary tables.

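### Section IX tabulates pre-dose brequinar and DHO by scheduled time point and only lists the actual dose-to-sample interval, so once-weekly and twice-weekly troughs can be pooled

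*SAP*

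**What the plan says.** Section IX gives the tabulation rule: "Concentration and PK parameters will also be tabulated and summarized by treatment group at baseline and scheduled time points using descriptive statistics". Its only stated use of actual timing for pre-dose samples is a listing: "A listing of derived time interval between Brequinar dosing and pre-dose PK sampling will be provided". It adds mean profiles by treatment group and by-subject plots, without saying whether the time axis is nominal or actual.

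Section IV.A makes dose frequency a subject-level decision. Cohort 2 starts once weekly. Week 2 results decide whether Week 3 is once or twice weekly, and the Week 2 procedures may be repeated until a twice-weekly dose is found. Two DHO times govern these decisions. The first governs the move to twice-weekly dosing: "After both the brequinar PK and 72-hour DHO level meet criteria described in the Individual Dose Adjustment Guidelines". The second governs later adjustment: "The twice-weekly dose may be further adjusted using 84-hour DHO (trough ~ 84 hours after dosing) criteria".

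Section VII.B shows trough DHO in a listing: "A subject listing will include baseline and trough DHO levels (ng/ml), as well as the following additional characteristics noted at each scheduled visit". Hours since the last dose are not among the items that follow.

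The data needed are collected. Section VII.A lists "dose day, date and time taken, whether entire dose was taken" for each dose, and the vendor transfer in Section V.A carries the date and time of each sample.

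**The concern.** A trough concentration is interpretable only with the time since the last dose. Here that time is not the same for all subjects by design, because some may be dosed weekly while others in the same cohort are dosed twice weekly. A table keyed to treatment group and scheduled time point does not separate them, unless treatment group or the time-point label encodes frequency. The SAP does not say that either does.

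Trough DHO indicates whether DHODH inhibition lasts until the next dose. DHODH inhibitory activity is part of the primary objective (Section II.A), and the relation of DHO level to safety and brequinar levels is a primary endpoint (Section III.A). Sections III.C, IX and X also foresee relating DHO or DHODH inhibition to efficacy and toxicity. If sampling interval differs between subjects and is ignored, a longer interval can look like weaker inhibition. Frequency itself depends on each subject's PK and DHO results, so interval and response would be entangled in any such exploration.

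**Working it through.** **1. The plan's own figure.** A week has 7 × 24 = 168 h. Two equally spaced doses give 168 / 2 = 84 h, which reproduces the trough time in Section IV.A. One dose per week gives a pre-dose interval of about 168 h.

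**2. Can both intervals fall under one label?** All Cohort 2 subjects start once weekly, so the Week 2 pre-dose sample follows the first dose by about 168 h. From Week 3 frequency can differ. A subject who has moved to twice-weekly dosing has later pre-dose samples at about 84 h. A subject who stays weekly, or repeats the Week 2 procedures, still has them at about 168 h. If scheduled time points are labelled by study week, the two share a row. The labels are in the protocol, so this is a possibility the SAP leaves open, not a certainty.

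**3. Spread within twice-weekly dosing (assumption).** Two doses per week at the same clock time cannot be 84 h apart. A 3-day/4-day pattern gives 3 × 24 = 72 h and 4 × 24 = 96 h, mean 84 h. The SAP gives neither dosing days nor clock times.

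**4. Illustrative size, brequinar only.** The SAP gives no half-life, so it is assumed. The model is mono-exponential decline after the same dose, ignoring carry-over from earlier doses. The ratio of an earlier to a later value is r = 2^(difference in hours / half-life). An equal mix of the two times alone adds a CV of (r − 1)/(r + 1).

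| Assumed half-life | C84/C168 = 2^(84/t½) | CV from equal mix | C72/C96 = 2^(24/t½) | CV from equal mix |
|---|---|---|---|---|
| 12 h | 2^7 = 128 | 127/129 = 98% | 2^2 = 4.0 | 3/5 = 60% |
| 24 h | 2^3.5 = 11.3 | 10.3/12.3 = 84% | 2^1 = 2.0 | 1/3 = 33% |
| 48 h | 2^1.75 = 3.4 | 2.36/4.36 = 54% | 2^0.5 = 1.4 | 0.41/2.41 = 17% |

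The equal mix is also an assumption. A less even split gives a different CV.

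**5. DHO.** DHO is a pharmacodynamic marker and need not decline mono-exponentially, so these ratios do not transfer to it. What the SAP does show is that the design treats 72 h and 84 h DHO, 12 h apart, as separate criteria. The gap between weekly and twice-weekly troughs is 168 − 84 = 84 h, seven times as wide.

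**6. Existing safeguards.** The PK Analysis Set (Section V.E) excludes subjects with important deviations or events affecting PK. It has no timing criterion, and a weekly trough taken on schedule is not a deviation. Section V.F keeps unscheduled and repeat measurements out of the tables, also without a timing criterion. Neither separates 84 h from 168 h.

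**The case against.** The strongest objection is that pooling is not demonstrated. The SAP tabulates by scheduled time point, and the schedule is in a protocol not at hand. On a regular 3-day/4-day pattern the two weekly pre-dose samples could be separate time points, which would put 72 h and 96 h values in different rows. Doses are oral, so a morning/evening split giving exactly 84 h is not excluded. The analyses are descriptive, Section IX says only that PK-DHO-outcome relations may be explored, and the listing lets a reader check any sample's timing.

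Most of this stands as a limit on the claim:

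- A reader might infer that samples labelled as 84 h troughs are really taken at 72 or 96 h. The SAP does not show that. Its only 72-hour figure is the criterion for moving to twice-weekly dosing, and 96 hours appears nowhere.
- A reader might apply the half-life ratios to trough DHO, or read the 84-hour label as a brequinar figure. The SAP attaches that label to DHO only and gives no decline model for it.
- A reader might infer that the non-compartmental parameters or by-subject plots use nominal times. The SAP does not say either way.
- Section IX names no dedicated trough table. Trough DHO by visit appears as a listing in Section VII.B.

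The objection does not remove the difference between weekly and twice-weekly dosing. That comes from Section IV.A itself, can arise within one cohort, and needs no assumption about weekdays or clock times. A listing allows checking, but it does not change a pooled mean or CV.

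**Conclusion.** The concern holds in a limited form. The SAP derives the interval that would make pre-dose values comparable, names only a listing for it, and tabulates by a label that can combine samples about 84 h and about 168 h after dosing. This rests on two conditions: that treatment group and time-point labels do not already encode dosing frequency (the SAP does not say that they do), and that some subjects remain weekly while others in the group have moved to twice weekly. A 72 to 96 h spread within twice-weekly dosing is a further possibility, not an established fact.

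The size for DHO is unknown from the SAP. For brequinar it could be a factor of 3.4 or more between the two frequencies at half-lives of up to 48 h, under the assumptions shown. No confirmatory test depends on these tables, but they describe a quantity in the primary objective, so the change is worth making before the analysis is run.

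**What to change.** In Section IX:

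- Keep the scheduled-time-point table. Beside it, summarize pre-dose brequinar and DHO by pre-specified windows of actual hours since the last dose, with windows covering both once-weekly and twice-weekly intervals.
- Flag samples outside every window and show them. Do not use windows confined to the twice-weekly range, which would drop valid once-weekly samples.
- Plot trough brequinar and trough DHO against actual hours since dose.
- Use the actual interval in any exploration of trough against efficacy or toxicity, for example by stratifying on it.

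It would also help to add hours since the last dose to the DHO listing in Section VII.B.

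The cost is SAP wording and a little more programming, since the interval is already to be derived and both clock times are collected. The downside is smaller cells: with about 6 subjects in Cohort 2 and about 15 in the expansion cohort, some windows will hold few values, so the plot may be more informative than the table.
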